10.2 CSF PROTEOMICS

Patient specimens

Participation in this component of the study is optional. Patients excluded from this biological study will include those in whom procurement of CSF is deemed unsafe by the attending physician and in those participants whose family declines the evaluation.

CSF will be obtained prior to initiation of any post-operative radiation therapy or cetuximab. CSF will be obtained via lumbar puncture, ventricular or cisternal sample at the time of flow diversion or aspiration of an external ventricular drain or surgical procedure. In patients where more than one site of CSF fluid has been accessed, analysis from each site will be undertaken when possible.

CSF cytology will be evaluated for presence of tumor cells by an institutional pathologist using standard methods. Approximately 3 ml of CSF will be requested for proteomic analysis. After acquisition, the CSF should be kept on wet ice or in a 4 degree refrigerator until processing. Processing should be performed within 6 hours of sample acquisition. The CSF will be spun at 400-500 g for 10 minutes to remove cellular contaminants. The first 2 ml of CSF supernatant will be aliquoted into four 500 mcl units (taking care to leave the cellular pellet behind) and frozen at -20 to -80 degrees Celsius to be used for proteomic analysis. Each tube must be labeled with the POETIC patient accession number, the sample type and the time it was drawn.

If sample is insufficient for both laboratories priority is to send sample to [name] collection and shipping dates must be documented in the clinical research core. These samples should be forwarded via FedEx, Monday through Thursday. No weekend deliveries are permitted. Sites should contact [name], at [contact] to notify of shipment. All CSF biologic samples should be shipped on dry ice, along with a completed biologic specimen transmittal form to:

> Attention: [name] [name] [contact] Email: [contact]

The remaining 1 ml of CSF will be aliquoted in 200 mcl units and frozen at -20 to -80 degrees Celsius to be evaluated for cytokines. Each tube must be labeled with the POETIC patient

accession number, the sample type, site from where the sample was obtained, and the time it was drawn.

These samples should be forwarded on dry ice via FedEx, Monday through Thursday to the following address:

Attn: [name] [name]

No weekend deliveries are permitted. Sites should contact [contact] to notify of shipment.

Laboratory analysis

a. Proteomic Biomarker Evaluation

Criteria for a successful proteomic methodology for identification of a usable biomarker include high throughput, reproducibility and toleration of real world collection and shipping conditions. In addition, such methods must be able to identify differentially expressed proteins in an unsupervised manner as well as provide information about specific proteins of interest. Currently, there is not a single mature technology available to meet all these criteria. Therefore, a combined approach will be employed in this exploratory study to attempt to fit all of these characteristics and improve the body of knowledge about the utility of these strategies.

All these approaches will require concentration and desalting of the samples. Proteins can be precipitated using 15% trichloracetic acid, re-suspended in denaturing buffer and stored at -20 to -80 degrees Celsius until the time of analysis.

The first component of the proteomic approach will employ 2-D gel electrophoresis to separated proteins in two dimensions according to their size and charge. The gels are then stained with Gelsoft coomasie stain (Bio-Rad) and then scanned by a high resolution scanner. Relative spot positions and intensities are quantitated by pixel reading software (PDQuest and Ludesi). Individual spots are normalized to total signal [Proteomics 2003; 3:1962-1979]. Individual proteins that are found to be differentially expressed between groups will be subjected to in-gel trypsin digestion. Published work at Children's National Medical Center with this methodology has successfully fractionated CSF derived proteins and identified differentially expressed proteins in white matter disease [Clin Chem 2005; 51:2031-2042].

The second approach employed will be label free quantification. MS-based proteome profiling is a powerful method by which a large number of proteins across large sets of complex samples can be identified. The main obstacle in protein profiling is to distinguish ('labels') proteins (at the peptide level) that are originated from different samples. New and emerging techniques such as stable isotope labeling (SILAC, iTRAQ, ¹⁸O) are either expensive (iTRAQ, SILAC) or unstable (¹⁸O). With the improvement of liquid chromatography (LC) as well as mass spectrometry (MS) techniques, the new trend in proteome profiling is label-free methodology. The idea behind this

method is first to generate reliable and reproducible LC-MS runs using trypsin digested proteins from CSF samples. In order to accommodate minor discrepancies between subsequent runs, each sample will be spiked with a known amount of non-native protein. Peaks generated by this protein will be used for internal normalization, as well as for normalization across sample sets. Given that peptides elute and behave similarly between different runs, peak heights (at MS or MS/MS stage) representing peptides can be extracted, calculated, and normalized to the internal (spiked) standard. From these data, differential protein expression can be calculated across inter/intra sample populations to identify potential biomarkers.

b. ELISA for confirmation/correlation of target proteins

CSF samples will be evaluated for expression of specific secreted proteins implicated in tumor progression, migration and response to therapy. These target proteins, described above, have well-characterized, commercially available antibodies including VEGF, dFGF, attractin, SPARC and EGF.

10.3 SERUM ANALYSIS OF INFLAMMATORY CYTOKINE LEVELS

Participation in this component of the study is optional.

Experimental design

Sera will be collected before the first dose of cetuximab and at the time of the development of the characteristic skin rash and at its distinct stages of progression. A scoring system will provide a standardized evaluation of the rash (Table 1).

Table 1 S	Simplified	classification	of acheiform	eruntion a	caused by EGFR inhibitors
	Junphilea	classification		cruption	caused by LOT R minoriors

NCI CTCAE v3.0								
Rash/desquamation								
Grade 1	Grade 2	Grade 3	Grade 4					
Lesions without symptoms	Lesions with symptoms < 50% body surface	Lesions with symptoms ≥ 50% body surface	Exfoliative, ulcerative or bullous erythroderma					
Rash: acne/acnef	orm							
Grade 1 Grade 2 Grade 3 Grade 4								
Intervention not indicated	Intervention indicated	Pain, disfigurement, ulceration or desquamation	-					

Using a sensitive antibody array technique, the presence of approximately 40 separate cytokines (Table 2) will be detected and quantified as described previously [Anal Biochem 2001; 294:55-62, http://www.raybiotech.com/principle.asp?m=6]. Briefly, blood will be collected at specified times and sera will be incubated with cytokine arrays that contain capture antibodies. Commercially available normal human sera will be used as additional control. Following three washing steps to remove unbound proteins, enzyme labeled detection antibodies will be added and the arrays will be developed using conventional ECL reagents. The resulting X-ray films will be scanned and analyzed by digital image processing. Significant changes will be validated by ELISA or Western blot analysis. Data will be analyzed using GraphPad Prism version 3.00 statistical software (GraphPad Software, San Diego, CA). Changes more than a standard deviation seen in normal sera will be considered significant. Correlative analysis will be carried out with clinical parameters indicated in the protocol.

EOTAXIN	GCSF	GM-CSF	ICAM-1	IFN-g	I-309	IL-1 ^a	IL-1b
IL-2	IL-3	IL-4	IL-6	IL-6sR	IL-7	IL-8	IL-10
IL-11	IL-12	p40	p70	IL-13	IL-15	IL-16	IL-17
IP-10	MCP-1	MCP-2	M-CSF	MIG	MIP-1a	MIP-1b	MIP-1d
MIP-1d	RANTES	TGF-b1	TNF-a	TNF-b	sTNFRI	sTNFRII	PDGF-BB
TIMP-2							

Table 2. Inflammation related cytokines to be analyzed in the sera of patients who develop rash during treatment on protocol.

Timing of sample collections

Blood will be collected from patients prior to the first dose of cetuximab in the phase I portion of the study as a control. Sera will also be collected from patients who do not develop rash prior to the first 4 cycles of irinotecan and cetuximab in the Phase II portion of the study. If a patient develops a rash at any point during the Phase I portion of the study or during cycles 1-3 of the Phase II portion of the study they are not to be considered a control subject anymore and are not to have any further precycles 1-4 blood samples taken. Additional samples will be drawn when there is an incremental increase in the severity score of the rash (see guidelines, Table 1). Specific information regarding the rash will be collected based on the key clinical features and classification of dermatologic adverse reactions of EGFR targeted agents described by Agero et al [J Am Acad Dermatol 2006; 55:657-670]. To minimize patient inconvenience, blood draws will be done to coincide with other routine blood draws or IV access.

Sample collection, processing and transport

Collect 1 ml of blood and allow for clotting on ice or in a refrigerator for approximately 15- 30 minutes. Separate and collect the serum, preferably in an Eppendorf microcentrifuge tube. If micro centrifuge tubes are not available, any cloudy plastic tube can be used. Sera will be separated from the clot by centrifugation (1,200 RPM for 5 minutes), transferred to an Eppendorf tube and stored frozen in a -20 C freezer until shipment.

Ship sera on dry ice by next day delivery. Send samples only on Monday through Thursday. Public holidays in Canada can be found in: http://www.pch.gc.ca/progs/cpsc-ccsp/jfa-ha/index_e.cfm

IRB#: 09-014 A(7)

The following information should be included with each sample:, Site ID, study number, study time point, date and time of collection. Please attach 3 copies of the completed customs form below on the outside of your shipment box. Shipments with less then 3 customs forms and are not located on the outside of the box will not be considered for shipment. Please send an email notification of the shipment including the tracking number to the following addresses: [contact], [contact]

Laboratory personnel will be available to answer questions regarding this process by phone at all times as indicated in the sample processing form.

Information for Customs Canada Form Date:

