9.4 SUPPORTIVE CARE

Clinical judgment may be used to alter the following guidelines without being a protocol violation:

During all phases of therapy

Anti-emetics may be used.

Filgrastim (G-CSF) may be used according to institutional practice and/or ASCO guidelines.

Patients developing dermatologic toxicities while receiving cetuximab should be monitored for the development of inflammatory or infectious sequelae, and appropriate treatment of these symptoms initiated. Dose modifications of any future cetuximab infusions should be instituted in case of severe (grade 3) acneform rash/desquamation (section 9.3.1). Treatment with topical and/or oral antibiotics should be considered; topical corticosteroids are not recommended. If a patient experiences severe acneform rash/ desquamation, cetuximab treatment adjustments should be made according to the table above (section 9.3.1). In patients with mild and moderate skin toxicity, treatment should continue without dose modification.

During the second phase of therapy (while patients are receiving irinotecan)

Anti-convulsants: Enzyme-inducing anti-convulsants (phenytoin, phenobarbital, carbamazepine) should be avoided. Patients who require an anti-convulsant should be treated with a non-enzyme inducing anti-convulsant for a minimum of 4 half-lives of the anti-convulsant agent prior to starting treatment with irinotecan. Documentation of this should be included on the Concomitant Medication form in the Case Report Forms.

Diarrhea: Prophylaxis with an oral cephalosporin (such as cefixime 8 mg/kg/day, maximum 400 mg/day) may be used [J Clin Oncol 2006; 24:563-570]. For early onset diarrhea (during irinotecan infusion or shortly after the infusion), consider atropine (0.01 mg/kg, maximum 0.4 mg) and octreotide. For later onset diarrhea, consider prompt use of loperamide, and consider octreotide if that does not adequately control diarrhea. Suggested loperamide (1 caplet = 2 mg, 1 teaspoon = 5 ml = 1 mg) dosing follows:

- Patients > 43 kg: Take 4 teaspoons or 2 caplets after the 1st loose bowel movement followed by 2 teaspoons or 1 caplet every 2 hours. During the night the patient may take 2 caplets every 4 hours rather than 1 caplet every 2 hours.
- Patients > 30 to 43 kg: Take 2 teaspoons or 1 caplet after the 1st loose bowel movement followed by 1 teaspoon or ½ caplet every 2 hours. During the night the patient may take 1 caplet every 4 hours rather than ½ caplet every 2 hours.

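### G-CSF is measured as an inflammatory cytokine while filgrastim (G-CSF) is permitted, and no rule stops a sample drawn soon after a dose from being scored as a significant change

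*Combined protocol and SAP*

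**What the plan says.** Section 10.3 describes an optional serum study. Its Table 2 is captioned "Inflammation related cytokines to be analyzed in the sera of patients who develop rash during treatment on protocol" and has GCSF as its second entry. The text says: "Using a sensitive antibody array technique, the presence of approximately 40 separate cytokines (Table 2) will be detected and quantified".

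The decision rule in the same section is "Changes more than a standard deviation seen in normal sera will be considered significant". The confirmation step is "Significant changes will be validated by ELISA or Western blot analysis".

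Sera are taken before the first cetuximab dose, when the rash appears, and each time its severity score rises. For controls, "Sera will also be collected from patients who do not develop rash prior to the first 4 cycles of irinotecan and cetuximab"; a patient who develops a rash leaves the control group. Each sample travels with site, study number, time point, and date and time of collection.

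Section 9.4, under the line "During all phases of therapy", states: "Filgrastim (G-CSF) may be used according to institutional practice and/or ASCO guidelines".

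Section 14.3.2 makes the biological endpoints exploratory and descriptive, with changes given from baseline in percent and absolute terms. Section 16.0 has concomitant drugs recorded in the general study data.

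**The concern.** The analyte and a permitted drug carry the same name in the protocol. Secondary objective 4 in section 2.0 asks whether the rash arises from an inflammatory pathway that cetuximab starts in host cells. A raised G-CSF value would count towards that explanation. If the patient had recently received filgrastim, the value may instead reflect supportive care.

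The baseline makes this worse. It precedes all protocol therapy, and section 6.2 excludes prior chemotherapy and radiation, so it is very likely free of filgrastim. A later exposed sample would then show injected drug as change from baseline. The error is confined to the G-CSF row of the results, but a reader of that row could not see it.

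**Working it through.** **1. The analyte list.** Table 2 has 41 cells. MIP-1d appears twice, leaving 40 distinct labels, or 39 analytes if the cells IL-12, p40 and p70 are read as two forms of IL-12. This agrees with the stated figure of about 40. GCSF is one of them: 1/40 = 2.5%, or 1/39 = 2.6%.

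**2. Is there a handling rule?** I looked for one in each place it could stand.
- Section 10.3, design: no exclusion, washout or adjustment for concomitant drugs.
- Section 10.3, confirmation: ELISA or Western blot would re-measure the protein. Neither is described as separating injected from endogenous G-CSF, so either could simply confirm the raised level.
- Section 10.3, sample information: no drug field.
- Section 14.3.2: medians, ranges and changes only.
- Section 16.0: concomitant drugs are recorded but not tied to this analysis.

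**3. What the one-SD rule does with a raised value.** Assume normality and let filgrastim raise the signal by k standard deviations of normal sera. Under reading A the change itself has SD 1, so the probability of an upward flag is 1 − Φ(1 − k). Under reading B the change is the difference of two independent draws, each with SD 1, so the probability is 1 − Φ((1 − k)/√2). The documents give no value of k, so a range is shown.

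| k | Reading A | Reading B |
|---|---|---|
| 0 | 0.16 | 0.24 |
| 1 | 0.50 | 0.50 |
| 2 | 0.84 | 0.76 |
| 3 | 0.98 | 0.92 |
| 5 | about 1.00 | about 1.00 |

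Under either reading, a rise of a few SD is nearly always flagged.

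**4. Which samples are exposed?** I take the two study portions named in 10.3 to be the two phases of therapy in section 9.
- *Early rash samples.* Adult data in section 11.2 put rash onset generally within two weeks of starting treatment. Here that falls in the radiation phase, before irinotecan. In the adult colorectal table of the same section, leukopenia of any grade was below 1% with cetuximab alone and 25% with irinotecan added. The usual reason for filgrastim is thus largely absent early on.
- *Rash appearing or worsening in the irinotecan phase.* The rash, not the treatment calendar, sets these draws, so they can fall at any point in a cycle. Section 11.3 lists neutropenia among irinotecan's serious effects. These samples are the most exposed.
- *Control draws before cycles 2 to 4.* Section 9.2 starts a cycle 21 days after the previous start, with ANC at least 1000/mcl. If irinotecan is given on days 1–5 and 8–12 (an assumption), a draw on day 21 or 22 comes 21 − 12 = 9 or 22 − 12 = 10 days after its last dose. That is a time of count recovery. Recent filgrastim is possible, since no filgrastim-free interval is required.
- *Control draw before cycle 1.* This phase begins 28 to 56 days after radiation, before any irinotecan and with the same ANC threshold. Exposure is unlikely.

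**The case against.** Filgrastim is permitted, not required. A problem arises only if a patient consents to the optional study, receives filgrastim, and is sampled while drug is still in the serum. A reader might infer that injected drug will be scored as a cytokine change. The documents support only that it can be, because they give no use rate.

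A reader might also infer that the no-rash controls are sampled when filgrastim use is likeliest, so that raised controls would hide a true rash effect. Section 9.2 does not support this. The control draws are pre-cycle, starting a cycle requires recovered counts, and the first draw precedes irinotecan. Masking through the later control draws remains possible, but it is not the main exposure.

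The data needed to find affected samples are largely collected already: collection date and time in 10.3 and concomitant drugs in 16.0. An analyst could annotate an odd G-CSF value without any rule. The one-SD threshold is also a larger source of noise. Under reading A with no drug effect, it flags 2 × (1 − Φ(1)) = 0.317 of analytes by chance, or 40 × 0.317 = 12.7 of 40.

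These arguments limit the size of the point but do not answer it. Descriptive status does not turn a drug level into biology, and section 10.3 would still label the change significant. Recorded drug data help only if someone is told to use them and dose dates are among them.

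**Conclusion.** The point holds as a minor gap in analysis handling. Followed as written, the plan can report a G-CSF value raised by filgrastim as a significant inflammatory change, and nothing in sections 10.3 or 14.3 prevents it. The direct effect is on one of about 40 analytes in an optional, descriptive component. The primary endpoint, the sample sizes and the toxicity stopping rule are untouched.

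The conclusion assumes that the array antibody detects filgrastim. The protocol gives both the same name but does not describe the antibody. It also assumes that some participants receive filgrastim close to a draw. A reader might want a fold-rise or a count of affected samples. The documents give no dose, clearance, endogenous level or frequency of use, so neither is claimed. Nor do they show that filgrastim moves the other cytokines; that is only a reason for a sensitivity check.

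**What to change.** Add a short rule to section 10.3:
- Link each serum sample's collection date and time to the concomitant-drug record, and make sure filgrastim dose dates are captured there. This needs attention because section 9.2 lets irinotecan be given at another center or through homecare, so related drug records may also originate off site.
- Treat G-CSF as missing, or report it separately, for samples drawn within a fixed interval after filgrastim. Set the interval, with its justification, before the arrays are read.
- Show the other cytokines with and without those samples.

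The cost is a few lines of analysis text, a check that dose dates are recorded, and a few missing G-CSF values. A separate field on the sample form is needed only if the drug record cannot supply the dates. Supportive care and the sampling schedule stay as they are.

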In cynomolgus monkeys, cetuximab, when administered at doses of approximately 0.4 to 4 times the weekly human exposure (based on total body surface area), resulted in dermatologic findings, including inflammation at the injection site and desquamation of the external integument.¹ At the highest dose level, the epithelial mucosa of the nasal passage, esophagus, and tongue were similarly affected, and degenerative changes in the renal tubular epithelium occurred. Deaths due to sepsis were observed in 50% (5/10) of the animals at the highest dose level beginning after approximately 13 weeks of treatment.

In clinical studies of cetuximab, dermatologic toxicities, including acneform rash, skin drying and fissuring, and inflammatory and infectious sequelae (eg, blepharitis, cheilitis, cellulitis, cyst) were reported. In patients with advanced colorectal cancer, acneform rash was reported in 89% (686/774) of all treated patients, and was severe (Grade 3 or 4) in 11% (84/774) of these patients. Subsequent to the development of severe dermatologic toxicities, complications including *S. aureus* sepsis and abscesses requiring incision and drainage were reported.

IRB#: 09-014 A(7)

Non-suppurative acneform rash described as "acne", "rash", "maculopapular rash", "pustular rash", "dry skin", or "exfoliative dermatitis" was observed in patients receiving cetuximab plus irinotecan or cetuximab monotherapy. One or more of the dermatological adverse events were reported in 88% (14% Grade 3) of patients receiving cetuximab plus irinotecan and in 90% (8% Grade 3) of patients receiving cetuximab monotherapy. Acneform rash most commonly occurred on the face, upper chest, and back, but could extend to the extremities and was characterized by multiple follicular- or pustular-appearing lesions. Skin drying and fissuring were common in some instances, and were associated with inflammatory and infectious sequelae (eg, blepharitis, cellulitis, cyst). Two cases of *S. aureus* sepsis were reported. The onset of acneform rash was generally within the first two weeks of therapy. Although in a majority of the patients the event resolved following cessation of treatment, in nearly half of the cases, the event continued beyond 28 days.

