14.3 SECONDARY BIOLOGICAL AIMS

14.3.1 Progression free and overall survival will be calculated using the methods of Kaplan and Meier, separately for the diffuse pontine and high-grade groups. The response rates will be provided along with their 95% confidence intervals for all patients receiving any study medication or radiation.

14.3.2 It is not known how many patients will agree to participate in the components of the study involving (1) correlation of molecular markers and tumor response to therapy, (2) CSF proteomics, and (3) serum inflammatory cytokine levels. These endpoints are exploratory in nature and any analyses will be purely descriptive. Continuous endpoints will be summarized using medians and ranges, categorical data will be tabulated. Changes in measurements will be given in terms of percent change from baseline and change in absolute value.

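### Section 10.3 calls any cytokine change above one undefined SD significant although 14.3.2 plans description only, and rash sera drawn during radiation have no same-phase no-rash comparator

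*Combined protocol and SAP*

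**What the plan says.** Section 10.3 measures about 40 serum cytokines by antibody array in patients who agree to take part. On the reference material it says: "Commercially available normal human sera will be used as additional control". The decision rule is: "Changes more than a standard deviation seen in normal sera will be considered significant". What happens to a flagged change is: "Significant changes will be validated by ELISA or Western blot analysis". The section names a software package and adds a correlative analysis against clinical parameters, without a method.

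Section 14.3.2 covers the same component: "These endpoints are exploratory in nature and any analyses will be purely descriptive". Continuous measurements are to be summarised by medians and ranges, and "Changes in measurements will be given in terms of percent change from baseline and change in absolute value".

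On sampling, section 10.3 asks for serum before the first cetuximab dose, when the rash appears, and at each increase in its severity. For comparison, "Sera will also be collected from patients who do not develop rash prior to the first 4 cycles of irinotecan and cetuximab" in the second phase. Control status can be lost: "If a patient develops a rash at any point during the Phase I portion of the study", or during cycles 1 to 3, the patient stops being a control and gives no further pre-cycle samples. I read the Phase I and Phase II portions named there as the two phases of therapy in section 9.

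**The concern.** Secondary objective 4 asks whether the rash arises from an inflammatory pathway set off by cetuximab. Two features of section 10.3 could lead to a firmer answer than the data allow.

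(a) The rule attaches the word significant to a threshold whose error rate nobody can state. The missing items are the test, the unit (patient or group), the scale (percent, absolute or array intensity), the number of normal sera, and whether the SD reflects variation between people or in the assay. Section 14.3.2 contains no such rule. If 10.3 is followed as written, chance changes could be reported as significant support for objective 4.

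(b) A rash serum drawn during radiation can be set against the same patient's baseline, but not against an on-treatment serum from a rash-free patient in the same phase. A change from baseline to rash could come from the rash process, radiation, the passage of time, or cetuximab exposure that affects every treated patient. A cytokine that rises in everyone on cetuximab, rash or not, would not tie the pathway to the rash.

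**Working it through.** **No figure to reproduce.** The documents give no alpha, power or sample size for this aim, and 14.3.2 says the number of participants is unknown. The only count is about 40 cytokines. Table 2 prints 41 entries, one of them twice, which agrees.

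**Inputs**
- From the documents: a threshold of one normal-sera SD (10.3) and about 40 cytokines (10.3).
- Assumed, because the documents do not give them: normal errors; flags in either direction; no true change; equal variance at both time points; within-patient correlation ρ; and k = patient SD divided by normal-sera SD.

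**Step 1: one value against the normal mean.** With no true difference and k = 1, P = 2 × [1 − Φ(1)] = 0.317. About 32% of null values exceed one SD.

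**Step 2: change between two samples from one patient.** In units of the normal-sera SD, the SD of a change is k√(2(1 − ρ)). So P(flag) = 2 × [1 − Φ(1 / (k√(2(1 − ρ))))]. The expected number flagged is 40 × P, which does not require the cytokines to be independent.

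For k = 1:

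| ρ | 1/√(2(1 − ρ)) | P(flag) | Expected of 40 |
|---|---|---|---|
| 0 | 0.707 | 0.480 | 19.2 |
| 0.5 | 1.000 | 0.317 | 12.7 |
| 0.8 | 1.581 | 0.114 | 4.6 |
| 0.9 | 2.236 | 0.025 | 1.0 |

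**Step 3: dependence on the undefined SD.** If the normal-sera SD is mostly assay variation, k exceeds 1. At k = 2 the expected counts at the same four correlations are 28.9, 24.7, 17.2 and 10.5. At k = 0.5 they are 6.3, 1.8, 0.06 and below 0.01.

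**Step 4: dependence on the unit.** Applied to the mean of 10 patients (an assumed number, k = 1), P = 2 × [1 − Φ(√10 / √(2(1 − ρ)))]. This is 0.025 at ρ = 0 (1.0 of 40) and 0.0016 at ρ = 0.5 (0.06 of 40). The same sentence can therefore be very lax or quite strict, depending on facts that 10.3 leaves out.

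**Step 5: the sampling schedule, set side by side**
- First phase (9.1.0): 33 fractions and 6 weekly cetuximab doses over about 6½ weeks. Section 10.3 gives a pre-cetuximab serum and rash-triggered sera. It gives no on-cetuximab serum for a patient without rash.
- Interval (9.2): 28 to 56 days after radiation ends.
- Second phase (9.2 and 10.3): no-rash sera before cycles 1 to 4, and rash-triggered sera.

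The earliest post-baseline no-rash serum thus comes after radiation and after the interval. No no-rash serum in 10.3 matches a rash serum drawn during radiation.

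**The case against.** The strongest reply on (a) is that this is mostly a matter of wording. The only stated consequence of a flag is a second assay, and 14.3.2 limits the analysis to description. That stands: the rule behaves as a laboratory screen, and a reader who infers that the plan intends formal significance claims for cytokines goes beyond the text. Two things remain. ELISA or Western blot confirms that the level was measured correctly, not that the change exceeds ordinary variation. And 10.3 still uses the word significant and adds a correlative analysis with no method. Section 10.3 also cites outside sources for the array method; they are not available here and might define the normalisation or the SD.

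It is also fair to say that the flag counts rest on assumed inputs. They show that the rate is unknown, not what it is.

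On (b), the contents of Appendix 2, the table of mandated observations, are not in the supplied text, so the point rests on 10.3. Sera taken at successive rash grades do allow a within-phase description by severity, which is some comparison, though not a no-rash one.

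Three stronger readings are tempting but not supported:
- A reader might infer that the rule is insensitive because a true one-SD shift in a group mean would be flagged only about half the time. That holds for any threshold equal to the true shift, so it shows no defect here.
- A reader might take the 87% adult rash rate in section 11.2 and conclude that almost no rash-free controls will remain. That rate comes from adult head and neck cancer, uses a broad definition that includes dry skin, and would have to be applied to an unknown number of participants.
- A reader might conclude that most rash sera will fall in the radiation phase, because 11.2 says "The onset of acneform rash was generally within the first two weeks of therapy". That statement describes adult colorectal patients treated without radiation. The documents give no timing for children on this regimen.

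**Conclusion.** The point holds at low severity. Section 10.3 and section 14.3.2 need to be brought into line: one labels changes significant on an undefined threshold, and the other plans description only. Under the per-patient assumptions with k = 1, chance flags run from about 19 to about 1 of 40 as the correlation goes from 0 to 0.9, and other values of k widen that range in both directions. The documents do not fix where in the range the trial would fall.

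The sampling point is a limit on interpretation. On the schedule in 10.3, baseline-to-rash changes during radiation cannot be called rash-specific, because radiation, time and general cetuximab exposure are not separated from rash. Second-phase rash and no-rash sera can still be compared with each other.

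The component is optional and exploratory. The primary endpoints, the sample size and the toxicity stopping rule are unaffected.

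**What to change.** (a) In section 10.3, replace the sentence containing the rule with: *Within-patient percent and absolute change from the pre-cetuximab sample will be summarised by median and range (14.3.2). A change above one SD of normal sera is used only to select cytokines for ELISA or Western blot and is not a finding of significance.* In the sentence on validation, replace the first two words with *Changes selected by this screen*. State that the correlative analysis is descriptive too. So that the screen can be reproduced, say whether it is applied per patient or per group, how many normal sera are used, and whether the SD is between-person or assay variation.

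(b) Add to section 10.3: *Rash and no-rash sera are compared only within the same treatment phase. Baseline-to-rash changes during radiation are described only and are not interpreted as rash-specific, because radiation, time and general cetuximab exposure cannot be separated from rash.* Check that Appendix 2 agrees with this schedule.

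Cost: text edits only, with no new samples, visits or assays. The price is that rash sera from the radiation phase support description only.
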